7.5. Study Product, Dosage and Mode of Administration

The product being studied is obeticholic acid, in tablet form, dosed at 5 mg to 10 mg once daily oral administration. The study drug is not provided nor administered by the Sponsor but is recorded by either administrative claim or registry eCRF. The total duration of exposure will range from 1 to 67 months.

7.6. Study Period

The total study period is estimated to be a maximum of 6.6 years based on a pre-index period of 12 months prior to the index date and a maximum follow-up period of 5.6 years after the index date. The OCA treatment evaluation period will be from 01 Jun 2016 (based on FDA approval on 27 May 2016) to 31 Dec 2021. The first date of prescription of OCA after failing UDCA treatment will be defined as the index date for OCA-treated PBC patients. The date of evidence of inadequate UDCA response or UDCA intolerance, as defined below, will be used as the index date for the non–OCA-treated comparator group. Each time a patient meets the UDCA inadequate response/intolerance definition or the definition of OCA initiation, as well as all other inclusion/exclusion criteria, they will contribute an index to the study. Therefore, patients may contribute multiple indices and may appear in both groups, though they may contribute at most one index to the OCA-treated group.

8. ASSESSMENT OF EFFICACY

8.1. **Primary Outcomes/Endpoints**

The selection of a composite primary endpoint was informed by previous regulatory interactions regarding the 747-301 (POISE) and 747-302 (COBALT) studies (see Table 1). For COBALT, the primary composite endpoint included all-cause death, liver transplant, hospitalization for hepatic decompensation (bleeding varices and hepatic encephalopathy), uncontrolled ascites, and Model for End-Stage Liver Disease (MELD) Score \geq 15. Of these endpoints, only MELD cannot be adequately assessed in the current databases. The MELD algorithm includes a measure of the international normalized ratio (INR). A review of the Komodo Health and the Global PBC registry databases revealed that, unlike hepatic laboratory measures such as ALP and TB, INR is not routinely collected in PBC patients. Therefore, the Sponsor did not include MELD \geq 15 as part of the composite endpoint for these studies.

COBALT included the endpoint of uncontrolled ascites, defined as diuretic-resistant ascites requiring therapeutic paracentesis at a frequency of at least twice in a month. In a study of the POISE LTSE with external controls (Perez 2021), the Sponsor modified this endpoint to be consistent with other decompensating events, ie, hospitalization for ascites. As the FDA Guidance on Real-world Data (US Food and Drug Administration 2021) states, "...outpatient data sources that do not include hospitalization data would generally not be appropriate for studying outcomes likely to result in hospitalization." To increase consistency in the measures of

hepatic decompensating events, the Sponsor has included ascites (including hepatic hydrothorax and spontaneous bacterial peritonitis), along with variceal bleeding and hepatic encephalopathy, as part of the "hospitalization for hepatic decompensation" endpoint.

	COBALT (747-302)	POISE (747-301) LTSE with External Controls	HEROES PBC (747-404/405)
All-cause death	Х	Х	Х
Liver transplant	Х	Х	Х
 Hospitalization for hepatic decompensation Variceal bleed Hepatic encephalopathy 	Х	Х	Х
Uncontrolled ascites	Х	X^{a}	Xª
MELD Score ≥15	Х		

Table 1:	Composite	Endpoints fo	r OCA l	PBC Studies

^a Specifies hospitalization for ascites

The following primary efficacy assessment will be measured as an as-treated time to first occurrence of one of the following events:

- All-cause death
 - Komodo Health: The Komodo Health data has been linked to the US National Death Index (NDI), and mortality will be recorded as date of death as recorded in the Index
 - Global PBC registry: Death and date of death are reported by the physician via electronic Case Report Form (eCRF) and recorded through the CASTOR trial platform
- Liver transplantation
 - Komodo Health: The Komodo Health data will be linked to the OPTN database to ascertain whether a patient has received a liver transplant and the date of transplant.
 - Global PBC registry: Liver transplant and date of transplant are reported by the physician via eCRF and recorded through the CASTOR trial platform.
- Hospitalization for hepatic decompensation
 - Komodo Health: Hospitalization for hepatic decompensation will be assessed by any hospital admission claim with the following International Classification of Diseases (ICD)-10 codes (in any position) for decompensating events
 - Variceal bleed: ICD-10: I85.01, I85.11, I86.4 and ICD-9: 456.1, 456.21, 456.8
 - Ascites: ICD-10: K70.11, K70.31, K71.51, R18.0, R18.8, J94.8, K65.2 and ICD-9: 567.23, 571.2, 789.51,789.59, 511.8, 567.23

- Hepatic encephalopathy: ICD-10: B15.0, B16.0, B16.2, B17.11, B19.0, B19.11, B19.21, K70.41, K72.11, K72.90, K72.91 and ICD-9: 572.2, 070.0, 070.20, 070.41, 070.6, 070.71; or utilization of lactulose and/or rifaximin.
- Global PBC registry: Hospitalization for hepatic decompensation and date of hospitalization are reported by the physician via eCRF and recorded through the CASTOR trial platform

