4.6.2. Known and Potential Risks of OCA

The risk profile of OCA use in PBC has been evaluated in clinical trials and observational studies, as well as from postmarketing experience (estimated cumulative patient exposure from marketing experience is 20,554 patient-years). The key risk for OCA is pruritus. Potential risks

include liver injury and atherosclerotic cardiovascular events secondary to changes in lipids. The following focuses on these risks in the context of PBC, the subject of these current studies. Additional information is available in the Investigator's Brochure.

Pruritus: In subjects with PBC, the most commonly reported TEAE across all treatment groups was pruritus, which is a frequent symptom experienced by subjects with cholestatic liver disease. The incidence of pruritus was higher in the OCA-treated subjects as compared with placebo-treated subjects. In a small proportion of patients, pruritus can be severe and significantly interfere with sleep and patient functioning. Patients with a history of pruritus as part of the underlying disease have a higher probability of pruritus with OCA treatment. Otherwise, the occurrence and severity of pruritus in an individual patient treated with OCA cannot be reliably predicted or prevented, in part because pruritus is a frequent clinical feature of the underlying disease. Pruritus has also been seen in patients participating in clinical trials of investigational use of OCA, including NASH, where pruritus is not a common symptom of the disease state. Pruritus is generally clinically manageable. Reducing OCA dose or transient dose or transient treatment interruption helps alleviate, and in some cases, even resolves it.

Liver Injury: Liver injury is an important potential risk for OCA. Risk factors for drug-induced adverse hepatic effects are in general poorly understood in patients with chronic liver disease. Pre-existing liver disease may not increase the risk of developing drug-induced liver injury (Chalasani 2014). In the US, OCA is contraindicated in adult patients with PBC with decompensated cirrhosis or a prior decompensation event and with compensated cirrhosis with clinical evidence of portal hypertension. OCA is also contraindicated in adult patients with PBC with complete biliary obstruction.

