7.3. Exclusion Criteria

A patient who meets **any** of the following criteria for a given index date is not eligible for inclusion:

- History or presence of other concomitant liver diseases before the index date (inclusive), including:
 - Acute or chronic hepatitis C virus infection
 - Acute or chronic hepatitis B infection

- Primary sclerosing cholangitis
- Active alcoholic liver disease
- Hepatocellular carcinoma
- Hepatorenal syndrome
- Hepatopulmonary syndrome
- Portopulmonary syndrome
- NASH
- History of non-skin malignancy or melanoma before the index date (inclusive)
- History of HIV before the index date (inclusive)
- Medical conditions that may cause non-hepatic increases in ALP:
 - Paget's disease during the 12-month period before the index date (inclusive)
 - Fractures within 3 months before the index date (inclusive)
- Patients with laboratory values indicative of hepatic decompensation or significant hepatobiliary injury before the index date (inclusive):
 - TB >3 mg/dL
 - ALP >10x ULN
 - ALT and/or AST >10x ULN
- History of liver transplant before the index date (inclusive)
- Evidence of OCA, fenofibrate, or bezafibrate use before the index date (inclusive)
- History or presence of any of the following hepatic decompensating events before the index date (inclusive):
 - Variceal bleeding
 - Ascites
 - Hepatic hydrothorax
 - Spontaneous bacterial peritonitis
 - Hepatic encephalopathy

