8.3. Exposure Variable

The exposure variable initiates at the OCA index date. In the Komodo database, OCA exposure will be assessed as date of first filled prescription and quantified as days supply. Discontinuation will be assessed by a gap of >90 days after previous days supply. Treatment exposure will be continued for 90 days after last days supply, after which the OCA-treated patient will be censored. In the Global PBC database, OCA exposure will be from the first physician reported utilization date to discontinuation date, plus 90 days. In this study, exposure can range from 1 to 67 months.

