10.3. Hypotheses

10.3.1. Primary Hypothesis

These studies are intended to assess whether there is a difference between patients treated with OCA and comparable OCA-eligible patients who are not treated with OCA in the time from index to the first occurrence of all-cause death, liver transplant, or hospitalization for hepatic decompensation.

Two-sided hypotheses are expressed in terms of:

- The null hypotheses (H₀) that the 2 hazard functions are the same, as determined by a hazard ratio (HR) equal to 1; that is, at every timepoint, the instantaneous event rates are the same for the OCA and control populations.
- The alternative hypothesis (H₁) that the 2 hazard rates are not the same ($HR \neq 1$).

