10.4. Determination of Sample Size

Using the sample size in the 2 populations (Section 6.2), the Sponsor computed power to detect treatment effects (relative hazards) of varying sizes, estimated using Cox proportional hazards regression. Computations are based on the formulae of Schoenfeld 1983. To account for confounding control due to the application of IP weights, the Sponsor inflated the variance from the Schoenfeld formula using factors derived by Shook-Sa 2020. It was conservatively assumed just one control observation per patient. In the Komodo Health data, a preliminary investigation found that approximately 395 patients who meet entry criteria will initiate OCA and that 5916 patients will contribute at least one record to the control group (UDCA nonresponders). In the Global PBC registry, the Sponsor expects to have 344 patients meeting entry criteria who initiate OCA, and 2200 who contribute at least one observation to the control group. Power in both cohorts was computed for relative hazards ranging from 0.5 to 0.9 with an alpha level of 0.05. The Sponsor considered baseline event rates during follow-up from 5% to 15% and variance inflation corresponding to mild confounding (VIF=1.05), moderate confounding (VIF=1.5), and strong confounding (VIF=2.0). In each study, power was plotted under these assumptions against a reference line of 80% power under moderate confounding (VIF=1.5) (Figure 2).

Under mild confounding, both studies will be well-powered to detect an HR of 0.5. For moderate confounding, the Komodo Health study will be adequately powered to detect HR of 0.5 for event rates >6%. The Global PBC registry will be adequately powered to detect event rates >8%. Under strong confounding, the Komodo Health study will be adequately powered to detect

HR of 0.5 for event rates >9%. The Global PBC registry will be adequately powered to detect event rates >11%. Power decreases for more moderate HRs. None of the studies under even the most favorable assumptions will be able to detect HRs of 0.9. The Sponsor notes that the assumptions made here are conservative; in particular, it is expected that many more than one control observation and that the addition of lab data from LabCorp (as noted in Section 6.2) will substantially increase the size of both groups in the Komodo Health study.

Figure 2: Power estimates by Hazard Ratio by Level of Confounding for Komodo Health (A) and Global PBC Registry (B).

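### Censoring at OCA discontinuation has no counterpart in controls, so a first decompensation managed outside hospital can remove OCA follow-up just before the event; this favours OCA, and no planned analysis would show it

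*Combined protocol and SAP*

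**What the plan says.** **Endpoint.** Section 8.1 says for Komodo: "Hospitalization for hepatic decompensation will be assessed by any hospital admission claim" carrying a listed code in any position. For encephalopathy, Sections 8.1 and 12.4.3 add use of lactulose and/or rifaximin as an alternative to the codes, without naming a care setting. In the registry the physician reports hospitalization for decompensation. At baseline, by contrast, Section 7.3 excludes a decompensating event with no setting required.

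**Censoring of OCA indices.** Section 8.3 says for Komodo: "Treatment exposure will be continued for 90 days after last days supply, after which the OCA-treated patient will be censored". For the registry it uses the discontinuation date plus 90 days. Section 10.2 adds three months from the point at which the discontinuation definition is met. In Komodo that definition already needs a gap of more than 90 days, so 10.2 can be read as about 180 days.

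**Censoring of control indices.** Sections 6.1 and 10.1.1 censor controls when they start OCA or a fibrate, disenroll or reach study end. Discontinuation censoring applies to OCA indices only.

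**Contraindication.** Section 4.6.2 states that in the US "OCA is contraindicated in adult patients with PBC with decompensated cirrhosis or a prior decompensation event"; Section 4.1 says the same.

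**Handling.** Sections 10.2 and 10.7 address informative censoring with baseline covariates only. Section 4.5.1 prefers as-treated to intent-to-treat. The one sensitivity analysis of the effect estimate (10.9) concerns unmeasured confounding.

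**The concern.** Take two patients with the same first outpatient ascites after index. The control stays at risk, and a later admission, transplant or death counts. The OCA patient, if OCA is stopped because of the ascites, is followed for only about 90 more days of event time. Follow-up with the worst prognosis is then lost from one arm. The reason for censoring arises after index, so baseline covariates cannot make it non-informative.

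The affected events are ascites in both sources, encephalopathy in the registry, and encephalopathy in Komodo unless the drug clause captures it. At stake is the primary hazard ratio: with no true effect it falls below 1, and the chance of a significant result favouring OCA exceeds 2.5%. Nothing planned would reveal this.

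**Working it through.** **1. The plan's own figures.** The plan gives no figure for this bias. Its power statement supplies the sample sizes and variance inflation used below. With power = Φ(√(d·p(1−p)/VIF)·|ln HR| − 1.96), d = rate × N and p = OCA share, at HR 0.5:
- Komodo (395 + 5916 = 6311; p = 0.0626), 6%, VIF 1.5: d = 379, power 76.0%. 80% is reached at 6.65%.
- Komodo, 9%, VIF 2.0: d = 568, power 80.8%.
- Registry (344 + 2200 = 2544; p = 0.135), 8%, VIF 1.5: d = 204, power 78.8%.
- Registry, 11%, VIF 2.0: d = 280, power 80.1%.

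Three of the four thresholds fall within 2 points of 80%. Komodo at 6% falls short, which has no bearing on this point.

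**2. How much later risk the lag retains.** Assume composite events follow an outpatient decompensation at 0.7 per year, with 15 days of supply left plus 90 days (105 days). The share of stoppers whose event falls before censoring is 1 − exp(−0.7 × 105/365) = 18%. With 15 + 180 days it is 1 − exp(−0.7 × 195/365) = 31%. The remainder is lost from the OCA arm but can still be seen in controls.

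**3. Simulation with no true effect.** From the documents: maximum follow-up 5.6 years, the 90-day rule, and discontinuation censoring in the OCA arm only. Assumed: direct composite events 2%/yr, outpatient-first decompensation 0.4 to 2%/yr, later events 0.7/yr, 50% or 100% of OCA patients stopping at decompensation, unrelated OCA stopping 15%/yr, exponential times, and a 105-day lag. Estimated Cox HR (simulation error about ±0.01):

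| Outpatient-first rate | 0.4%/yr | 1%/yr | 2%/yr |
|---|---|---|---|
| Half stop | 0.97 | 0.92 | 0.87 |
| All stop | 0.93 | 0.84 | 0.74 |
| Half stop, drug clause captures 40% | 0.98 | 0.96 | 0.92 |
| All stop, drug clause captures 40% | 0.96 | 0.91 | 0.87 |

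The 40% is also an assumption. If nobody stops at decompensation, the HR is 1.00. If decompensation in any setting counts, or OCA indices are followed past discontinuation, it is also about 1.00.

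A wider grid of 48 settings (direct events 1.5–3%/yr, outpatient-first 0.5–3%/yr, later events 0.3–1.2/yr, half or all stopping, lag 90 or 180 days, no drug clause) gave 0.63 to 0.99, always below 1. In its central case (2%, 2%, 0.6/yr, all stop) the HR was 0.73 at 90 days and 0.79 at 180 days, and a true HR of 0.70 read 0.52.

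**4. False-positive chance, Komodo.** The sample-size section expects "approximately 395 patients who meet entry criteria will initiate OCA and that 5916 patients will contribute at least one record to the control group". At a 5% event rate, d₁ = 0.05 × 395 ≈ 20 and d₀ = 0.05 × 5916 ≈ 296. With the plan's VIF of 1.5, SE = √(1.5 × (1/20 + 1/296)) = 0.283. P(significant in favour of OCA) = Φ(−1.96 − ln HR/SE):
- HR 0.92: Φ(−1.96 + 0.295) ≈ 5%.
- HR 0.74: Φ(−1.96 + 1.064) ≈ 19%.
- HR 0.72: Φ(−1.96 + 1.161) ≈ 21%.

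The nominal value is 2.5%. The bias does not shrink with sample size. If LabCorp linkage doubles both groups, SE = 0.200 and the chance is about 6% at HR 0.92 and 32% at HR 0.74.

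**The case against.** **Stopping is inferred.** No rule censors at an outpatient decompensation; OCA must actually be stopped, and events within the lag still count. This stands. A reader might infer that every such event removes an OCA patient, but the documents do not say so.

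**The contraindication is narrow.** It is stated for the US and is not dated within 2016–2021. Section 4.6.1 mentions a US label update on 26 May 2021 and OCA trials that included decompensated patients, so the restriction may not have applied throughout. The registry spans 8 countries in Europe and North America. This stands and makes the argument weaker for the registry.

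**The drug clause.** A reader might take Section 8.1 to mean that nothing outpatient ever counts. Read literally, an outpatient lactulose or rifaximin fill is a Komodo event. That narrows the problem but does not reach ascites or the registry.

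**The endpoint.** A reader might place the fault in the hospitalization endpoint. Section 8.1 justifies it by prior regulatory interactions and consistency across decompensating events, and following OCA indices past discontinuation restores HR 1.00 with the endpoint unchanged. The cause is informative as-treated censoring.

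**The size.** The outpatient-first share, stopping rate and later event rate are all assumed. False-positive figures near 30% at the present Komodo size need both the extreme HR of 0.72 and omission of the plan's own variance inflation.

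**Conclusion.** The point holds as a should-fix for the sensitivity analyses. The asymmetry is in the text. It favours OCA whenever some OCA patients stop at a decompensation that is not itself counted, and the planned adjustment cannot remove it.

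The size is illustrative. Under the assumptions in the table, a null HR reads about 0.74 to 0.97, or about 0.86 to 0.99 with the drug clause capturing 40% (rounded outward for simulation error). A longer lag generally reduces the bias. At VIF 1.5 and about 20 OCA events, the false-positive chance in favour of OCA is about 5% at HR 0.92 and about 20% at HR 0.72 to 0.74. The argument is strongest for Komodo.

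A reader might conclude that the primary analysis must change. The documents do not establish that. Suspending discontinuation censoring only after a post-index decompensation would mix two estimands, and patients who stop while worsening but before a coded event would still be censored.

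**What to change.** Keep the primary endpoint and primary censoring. Before outcomes are unblinded (Section 10.1.2), add to Section 10.9:

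(a) An analysis that does not censor at OCA discontinuation and follows OCA indices to the composite event, disenrollment or study end. The alternative is time-varying inverse-probability-of-censoring weights that include post-index decompensation and laboratory values.

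(b) An analysis in which the first decompensation in any setting is the event in both arms, for example two outpatient claims on separate days or one inpatient claim in Komodo, and the clinical-event eCRF in the registry. Use one reconciled code list: for variceal bleeding, Section 8.1 lists ICD-9 456.1 and 456.21, which Appendix A describes as varices without bleeding, while the Appendix A exclusions list 456.0.

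State that a primary result not supported by (a) and (b) will be interpreted with caution. State the care setting for the lactulose/rifaximin clause in Sections 8.1 and 12.4.3, and reconcile the lag in 8.3 with that in 10.2.

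The cost is SAP wording and two analyses. Komodo already holds inpatient and outpatient claims (12.1.1), and Section 7.3 already requires decompensation to be identified. Downsides: (a) includes some off-drug time in the OCA arm, and (b) relies on less specific outpatient codes. Clinical care is unaffected.

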As the probabilities used to construct the weights are not known, they will be estimated using a logistic regression model. The model will be fit using observed treatment as the outcome and main effect terms for each of the covariates. Covariates (assessed in the pre-index period) will include:

- Age at index date
- Sex
- Most recent liver biochemistry levels (TB, ALP, ALT, AST)
- Most recent platelet counts
- Time (in months) since UDCA failure
- Clinical evidence of portal hypertension (platelets <150,000 and/or non-bleeding varices)
- Cirrhosis
 - Komodo Health: cirrhosis diagnosis with liver imaging and/or biopsy within 6 months before diagnosis
 - Global PBC registry: biopsy stage 4, transient elastography ≥16.9 kPa, radiological evidence (nodular liver or enlargement of portal vein with splenomegaly), clinical features of portal hypertension defined as platelet count <140 000/mm³ with persistent decrease in serum albumin; or, TB >2x ULN, or prothrombin time/INR > ULN (not due to antithrombotic use)
- Most recent Charlson Comorbidity Index Score (Glasheen 2019)
- Insurance type at the index date (Komodo Health only: commercial, Medicare, Medicaid, dual eligible, other)

All diagnosis, procedure and laboratory codes used to define the control variables are listed in Appendix A.

Once the weights are constructed, a table of weighted SMDs between the groups will be constructed to assess balance. An absolute SMD of greater than 0.1 will indicate potentially problematic residual imbalance for the particular covariate. In the case that either the model-fitting algorithm fails to converge, or residual imbalance exists after weighting, the study team will attempt to reduce model complexity or reduce imbalances by implementing one or more of the following actions:

- Adding/removing interaction terms (1st order or higher)
- Using a spline for continuous variables
- Shrinking all coefficients in the model using a penalty

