12.4.3. Komodo Health Hospitalization for Hepatic Decompensation

The primary endpoint is a composite of all-cause death, liver transplant, and hospitalization for hepatic decompensation. The primary source for hospitalization for hepatic decompensation will be Komodo Health claims. The definition will include inpatient admission ICD-10 codes that appear in any position, and includes:

- Variceal bleed: ICD-10: I85.01, I85.11, I86.4 and ICD-9: 456.1, 456.21, 456.8
- Ascites: ICD-10: K70.11, K70.31, K71.51, R18.0, R18.8, J94.8, K65.2 and ICD-9: 567.23, 571.2, 789.51,789.59, 511.8, 567.23
- Hepatic encephalopathy: ICD-10: B15.0, B16.0, B16.2, B17.11, B19.0, B19.11, B19.21, K70.41, K72.11, K72.90, K72.91 and ICD-9: 572.2, 070.0, 070.20, 070.41, 070.6, 070.71; or utilization of lactulose and/or rifaximin

As ICD-10 codes are standard across the US healthcare industry, there is no need for further harmonization across contributing health plans.

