814	ICD9	Fracture of carpal bone(s)
815	ICD9	Fracture of metacarpal bone(s)
816	ICD9	Fracture of one or more phalanges of hand
817	ICD9	Multiple fractures of hand bones
818	ICD9	Ill-defined fractures of upper limb
819	ICD9	Multiple fractures involving both upper limbs and upper limb with rib(s) and sternum
820	ICD9	Fracture of neck of femur
821	ICD9	Fracture of other and unspecified parts of femur
822	ICD9	Fracture of patella
823	ICD9	Fracture of tibia and fibula
824	ICD9	Fracture of ankle
825	ICD9	Fracture of one or more tarsal and metatarsal bones
826	ICD9	Fracture of one or more phalanges of foot
827	ICD9	Other multiple and ill-defined fractures of lower limb
828	ICD9	Multiple fractures involving both lower limbs lower with upper limb and lower limb(s) with rib(s) and sternum
829	ICD9	Fracture of unspecified bones

CODE	ТҮРЕ	DESCRIPTION
I85.01	ICD10	Esophageal varices with bleeding
I85.11	ICD10	Secondary esophageal varices with bleeding
456.0	ICD9	Esophageal varices with bleeding
K70.11	ICD10	Alcoholic hepatitis with ascites
K70.31	ICD10	Alcoholic cirrhosis of liver with ascites
K71.51	ICD10	Toxic liver disease with chronic active hepatitis with ascites
R18.0	ICD10	Malignant ascites
R18.8	ICD10	Other ascites
571.2	ICD9	Alcoholic cirrhosis of liver
789.51	ICD9	Malignant ascites
789.59	ICD9	Other ascites
J94.8	ICD10	Other specified pleural conditions
511.8	ICD9	Other specified forms of pleural effusion, except tuberculous
567.23	ICD9	Spontaneous bacterial peritonitis
K65.2	ICD10	Spontaneous bacterial peritonitis
B15.0	ICD10	Hepatitis A with hepatic coma
B16.0	ICD10	Acute hepatitis B with delta-agent with hepatic coma
B16.2	ICD10	Acute hepatitis B without delta-agent with hepatic coma
B17.11	ICD10	Acute hepatitis C with hepatic coma
B19.0	ICD10	Unspecified viral hepatitis with hepatic coma
B19.11	ICD10	Unspecified viral hepatitis B with hepatic coma
B19.21	ICD10	Unspecified viral hepatitis C with hepatic coma
K70.41	ICD10	Alcoholic hepatic failure with coma
K72.11	ICD10	Chronic hepatic failure with coma
K71.11	ICD10	Toxic liver disease with hepatic necrosis, with coma
K72.01	ICD10	Acute and subacute hepatic failure with coma
K72.91	ICD10	Hepatic failure, unspecified with coma
572.2	ICD9	Hepatic encephalopathy
070.0	ICD9	Viral hepatitis A with hepatic coma
070.21	ICD9	Viral hepatitis B with hepatic coma, acute or unspecified, with hepatitis delta
070.20	ICD9	Viral hepatitis B with hepatic coma, acute or unspecified, without mention of hepatitis delta

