070.2	ICD9	Viral hepatitis b with hepatic coma
070.6	ICD9	Unspecified viral hepatitis with hepatic coma
070.4	ICD9	Other specified viral hepatitis with hepatic coma
070.41	ICD9	Acute hepatitis C with hepatic coma
070.6	ICD9	Unspecified viral hepatitis with hepatic coma
070.71	ICD9	Unspecified viral hepatitis C with hepatic coma
Z48.23	ICD10	Encounter for aftercare following liver transplant
V42.7	ICD9	Liver transplant status
T86.40	ICD10	Unspecified complication of liver transplant
T86.41	ICD10	Liver transplant rejection

CODE	ТҮРЕ	DESCRIPTION
T86.42	ICD10	Liver transplant failure
T86.43	ICD10	Liver transplant infection
T86.49	ICD10	Other complications of liver transplant
996.82	ICD9	Complications of transplanted liver

COVARIATE CODES (INLCUDING CHARLESON COMORBIDITY INDEX

CODE	TYPE	DESCRIPTION
K76.6	ICD10	Portal hypertension
572.3	ICD9	Portal hypertension
I86.4	ICD10	Gastric varices
456.8	ICD9	Varices of other sites (non-specific)
I85.00	ICD10	Esophageal varices without bleeding
I85.10	ICD10	Secondary esophageal varices without bleeding
456.1	ICD9	Esophageal varices without mention of bleeding
456.21	ICD9	Esophageal varices in diseases classified elsewhere, without mention of bleeding
K74.5	ICD10	Biliary cirrhosis, unspecified
K74.60	ICD10	Unspecified cirrhosis of liver
K74.69	ICD10	Other cirrhosis of liver
571.5	ICD9	Cirrhosis of liver without mention of alcohol
I21	ICD10	Acute myocardial infarction
I22	ICD10	Subsequent ST elevation and non-ST elevation myocardial infarction
I25.2	ICD10	Old myocardial infarction
410	ICD9	Acute myocardial infarction
412	ICD9	Old myocardial infarction
I11.0	ICD10	Hypertensive heart disease with heart failure
I13.0	ICD10	Hypertensive heart and chronic kidney disease with heart failure and stage 1 through stage 4 chronic kidney disease, or unspecified chronic kidney disease
I13.2	ICD10	Hypertensive heart and chronic kidney disease with heart failure and with stage 5 chronic kidney disease, or end stage renal disease
I25.5	ICD10	Ischemic cardiomyopathy
I42.0	ICD10	Cardiomyopathy
I42.5	ICD10	Other restrictive cardiomyopathy
I42.6	ICD10	Alcoholic cardiomyopathy
I42.7	ICD10	Cardiomyopathy due to drug and external agent
I42.8	ICD10	Other cardiomyopathies
I42.9	ICD10	Cardiomyopathy, unspecified
I43	ICD10	Cardiomyopathy in diseases classified elsewhere
I50	ICD10	Heart failure
P29.0	ICD10	Neonatal cardiac failure
398.91	ICD9	Rheumatic heart failure (congestive)
402.01	ICD9	Malignant hypertensive heart disease with heart failure

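### Komodo (747-405): the variceal-bleed event list counts codes that Appendix A describes as varices without bleeding and omits a bleeding code, and the decompensation event and exclusion lists do not match

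*Combined protocol and SAP*

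**What the plan says.** Sections 8.1 and 12.4.3 give identical Komodo event lists. The bleeding component reads "Variceal bleed: ICD-10: I85.01, I85.11, I86.4 and ICD-9: 456.1, 456.21, 456.8". On where a code must appear, Section 12.4.3 says: "The definition will include inpatient admission ICD-10 codes that appear in any position". The encephalopathy component lists diagnosis codes that include K72.90 and K72.91, then adds "or utilization of lactulose and/or rifaximin".

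Section 7.1 says that Appendix A lists all codes used to define study variables. There, I86.4 is described as "Gastric varices" and 456.21 as "Esophageal varices in diseases classified elsewhere, without mention of bleeding". Code 456.1 is likewise described as not mentioning bleeding, and 456.8 as non-specific varices of other sites. All four are in the covariate table and none is in the exclusion table. The exclusion table has 456.0 (bleeding esophageal varices), K71.11 ("Toxic liver disease with hepatic necrosis, with coma") and K72.01 ("Acute and subacute hepatic failure with coma"). None of these three is an event code.

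Section 7.3 excludes patients with prior variceal bleeding, ascites, hydrothorax, spontaneous bacterial peritonitis or encephalopathy, the same conditions that form the endpoint. Non-bleeding varices do not exclude; Section 10.1.1 makes them part of a covariate: "Clinical evidence of portal hypertension (platelets <150,000 and/or non-bleeding varices".

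**The concern.** The endpoint is a hospitalization for a bleed, but four of the six codes that define it do not say that bleeding occurred. Read literally, an eligible patient with known gastric varices who is admitted for any reason, with I86.4 in any diagnosis position, has reached the primary endpoint and leaves follow-up. A patient with K72.90 before index is not excluded by that code and can have the same code counted as a new event later.

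At stake are the specificity of the Komodo primary endpoint and the interpretation of its hazard ratio. Section 10.9 plans bias analysis for unmeasured confounding and Section 10.10 examines the PBC diagnosis; neither addresses misclassified outcomes. The registry study (747-404) is not affected, because its events are physician-reported on the eCRF.

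**Working it through.** **Step 1: compare the lists.** Inputs are the event codes in 8.1/12.4.3 and the decompensation block of the exclusion table in Appendix A (liver transplant codes left out, duplicates counted once).

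| Component | Event codes | Exclusion codes | Shared | Event only | Exclusion only |
|---|---|---|---|---|---|
| Variceal bleed | 6 | 3 | 2 | I86.4, 456.1, 456.21, 456.8 | 456.0 |
| Ascites | 12 | 12 | 12 | none | none |
| Encephalopathy | 17 | 21 | 16 | K72.90 | K71.11, K72.01, 070.2, 070.21, 070.4 |
| Total | 35 | 36 | 30 | 5 | 6 |

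For ICD-10 alone there are 21 event and 21 exclusion codes with 19 shared. The mismatches are I86.4 and K72.90 (event only) and K71.11 and K72.01 (exclusion only). All four event-only variceal codes are Appendix A covariate codes. Five-character K72.90 is not in Appendix A; only its parent K72.9, unspecified hepatic failure, appears, as a covariate code.

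**Step 2: reproduce the plan's power basis.** Section 10.4 uses 395 OCA and 5916 control patients, the Schoenfeld formula and a variance inflation factor (VIF).

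Power = Φ(|ln HR| × √(D·p(1−p)/VIF) − 1.96), with p = 395/6311 = 0.0626 and D = 5916 × control rate + 395 × OCA rate.

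At HR 0.5 and VIF 1.5, power is 74.7% at a 6% control rate and 80.9% at 7%; 80% is reached at 6.8%. This agrees broadly with the plan's statement that Komodo is adequately powered above 6%. The illustration uses 7%.

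**Step 3: illustrate false events.** Let f be the false share of observed control events. It is an assumption, since the documents give no code frequencies. The true HR is 0.5.

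*(a) Same absolute false rate in both arms.* At f = 10% the control rate is 6.3% true + 0.7% false = 7%, and the OCA rate is 3.15% + 0.7% = 3.85%. The HR reads 3.85/7 = 0.55. D = 5916 × 0.07 + 395 × 0.0385 = 429, so power is 68.8%. With the false events removed, D = 5916 × 0.063 + 395 × 0.0315 = 385 and power is 76.7%.

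*(b) Same false share in both arms.* The HR stays at 0.50. D = 5916 × 0.07 + 395 × 0.035 = 428 and power is 80.9%. Removing the false events again gives D = 385 and 76.7% at f = 10%.

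*(c) Different shares.* HR = 0.5 × (1 − f0)/(1 − f1), where f0 and f1 are the false shares of observed control and OCA events.

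| f | (a) HR as written | (a) power as written | (b) HR, power as written | (a) and (b) power after cleaning | (c) false in control only | (c) false in OCA only |
|---|---|---|---|---|---|---|
| 5% | 0.525 | 75% | 0.50, 81% | 79% | 0.475 | 0.53 |
| 10% | 0.55 | 69% | 0.50, 81% | 77% | 0.45 | 0.56 |
| 20% | 0.60 | 55% | 0.50, 81% | 72% | 0.40 | 0.625 |

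At f = 10%, pattern (a) gives 83% as written against 90% cleaned at VIF 1.05, and 56% against 64% at VIF 2.0. All cleaned figures assume that only false events are removed.

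**The case against.** The strongest reply is that the code mismatch does not establish a harmful effect. A reader might infer that the extra codes must pull the hazard ratio toward 1 and cost power. That holds only for equal absolute false rates. If variceal admissions track true disease risk, the false shares may be similar in the two arms; the HR is then undisturbed, and cleaning costs about 4 points of power at a 10% share. This objection stands. A reader might instead infer that the codes favor OCA. The documents do not support that either. US labeling contraindicates OCA in compensated cirrhosis with portal hypertension (Sections 4.1 and 4.6.2), so varices may influence treatment choice, and balancing a covariate that combines platelets with varices does not guarantee balance on varices. But nothing fixes the direction.

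Three further readings go too far:

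- K71.11 and K72.01 need not be errors. An exclusion list broader than the event list can be deliberate; it is simply unexplained. Any missed event is also narrow: a non-fatal admission with no other qualifying code and no lactulose or rifaximin use.
- Outpatient lactulose or rifaximin use is not plainly an event. Both sections place that criterion under a hospital-admission rule. What is missing is an explicit statement of this and a rule for use before index.
- The ICD-9 errors cannot be shown to be negligible. Index dates from 01 Jun 2016 suggest few such events, but the documents give no date for the coding change, and Section 12.1.1 says the data hold both code systems.

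It is also fair that the Clean Room Committee may change variable definitions while blinded (Sections 10.1.2 and 10.11). That offers a route to correction; it does not correct the text. None of these replies explains a bleed list that includes codes described as non-bleeding and leaves out 456.0.

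**Conclusion.** The Komodo variceal-bleed definition is wrong as written against Appendix A's own descriptions, and following it exactly would count non-bleeding varices as primary events in patients who are eligible by design. The different handling of K72.90 before and after index is a second inconsistency. K71.11/K72.01 and the lactulose/rifaximin criterion need explanation rather than a presumed correction.

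Confidence is high for the mismatch and low for its consequence. The illustrated results, a loss of about 8 points of power, no distortion of the HR, or a shift in either direction, depend wholly on the assumed false shares and their pattern across arms. The point should be settled before outcomes are opened, because the same correction made afterwards could look outcome-driven.

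**What to change.** Before the event file is released:

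1. In Sections 8.1 and 12.4.3, remove 456.1, 456.21 and 456.8 from variceal bleed and add 456.0. Count I86.4 only when the same admission also carries a gastrointestinal bleeding code from a list fixed while blinded. The list must cover gastric bleeding, because the other ICD-10 bleed codes, I85.01 and I85.11, are esophageal. Apply the same rule in the baseline exclusion block, and run one sensitivity analysis under the plan's current I86.4 rule.
2. Treat K72.90 the same before and after index, either by adding it to the exclusions or by removing it from the events, and give the reason.
3. As options: align K71.11 and K72.01 or state why they differ; state that the lactulose/rifaximin criterion requires an admission and how use before index is handled.

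The cost is code-list and wording edits that the blinded committee can approve, plus one extra analysis. The statistical price is fewer counted events, possibly including true gastric bleeds coded only as I86.4, a loss that the figures above do not model. Whether power rises (69% to 77%) or falls (81% to 77%) at a 10% false share depends on the error pattern.
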